5.3 Dosage and Administration

Tazemetostat must be dispensed or administered only to subjects enrolled in the study and in accordance with the protocol. Standard institutional procedures for administering an oral agent via by mouth will be followed. An adequate supply will be provided with instructions on home administration.

Tazemetostat administered to newly enrolled subjects: Based on benefit-risk assessment of the population studied in this clinical trial, following a report of CCI in a pediatric patient, from the time Amendment 7.0 approval to the completion of enrollment, the following doses will be the starting dose for new enrolled patients: For new patients with ATRT or any INI1-negative tumors with CNS involvement, the starting dose will remain 1200 mg/m² BID. For new patients that are non-ATRT, the starting dose will be 520 mg/m² BID. (See Section 6.5.3).

Tazemetostat administered as an oral suspension: The starting dose of tazemetostat (for dose escalation only) will be 240 mg/m²/dose given BID (based on free base) = 480 mg/m²/day. The amount of suspension per dose is calculated based on the subject's body surface area (BSA) and the assigned dose level. After the completion of Cycle 1, if a subject is unable to continue dosing with the oral suspension formulation due to adherence issues, the Medical Monitor should be contacted to discuss the possibility of switching to tablet dosing options.

Tazemetostat administered as a tablet (subjects in Cohort 4 only; Cohort 4 is closed to enrollment): Tazemetostat will be orally administered at the dose of 800 mg/m² TID (2400 mg/m²/day). Please see CCI for tablet dosing nomogram. This will provide instruction on the number of tablets to be taken based on BSA. After the completion of Cycle 1, if a subject is unable to continue dosing TID with the tablet formulation because of the quantity of tablets or schedule, the Medical Monitor should be contacted to discuss the possibility of switching to BID tablet dosing or BID suspension dosing.

For subjects on the tazemetostat BID oral suspension schedule, doses should be administered as close to 12 hours apart as possible, but there should be no less than 8 hours between doses. For subjects on the TID tablet schedule, doses should be administered as close to 8 hours apart as possible, but there should be no less than 4 hours between doses. Doses may be taken with or without food.

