6.5 Dose Modification

During dose escalation, dose modifications are not allowed during Cycle 1. Any AE that is severe enough (at the discretion of the Investigator and with permission of the Sponsor/Medical Monitor) to warrant a dose reduction during Cycle 1 will be discussed with the Medical Monitor prior to resumption of study treatment.

Subjects who have an interruption in treatment for >14 days may restart treatment with tazemetostat after consultation with the Medical Monitor.

For any case of CCI /T-ALL, MDS/AML, or other myeloid malignancies like MPN, tazemetostat will be discontinued and the patient will be followed until resolution of the event.

No dose modification is required for the following Grade 3 or greater non-hematologic toxicities:

- Transient fatigue or asthenia
- Transient myalgia or arthralgia
- Nausea that resolves to <Grade 2 within 7 days (with or without anti-emetics)
- Vomiting that resolves to <Grade 2 within 48 hours (with or without anti-emetics)
- Diarrhea that resolves to <Grade 2 within 48 hours

For subjects in the dose-escalation portion of the study, refer to Table 4 for a description of dose levels to be used for dose modification. For example, a dose reduction of one dose level for a subject on a dose of 1200 mg/m² BID would be 900 mg/m² BID and that for a subject at a dose of 900 mg/m² BID would be 700 mg/m² BID.

For subjects on the dose expansion portion of the study, refer to Section 5.3 for new patient dosing levels.

- For subjects starting at 1200 mg/m² BID, refer to Table 6, below, for a description of dose level modifications.
- For subjects on the tablet formulation (Cohort 4), refer to CCI for instructions on how to administer tablets for each dose level.

Table 6. Dose Modification/Dose Reduction for Dose Expansion Portion

Starting Dose	1200 mg/m ² BID - OR - discontinue
Dose Level - 1	900 mg/m ² BID - OR - discontinue
Dose Level - 2	700 mg/m ² BID - OR - discontinue
Dose Level - 3	520 mg/m ² BID - OR - discontinue

- For subjects starting at the 520 mg/m² BID dose level in the dose expansion portion, no dose modifications are permitted. For these subjects, dosing may be interrupted for up to 14 days to allow resolution of AEs, and subjects must be discontinued if the AE does not resolve with dose interruption.

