6.5.1 Dose Modification due to Toxicity Not Related to Bromide

Other toxicities that, in the opinion of the Investigator are possible, probably, or definitely related to study treatment, should be managed per [Table 5](#). Toxicities that are felt by the Investigator to be unrelated to tazemetostat but clinically significant should be discussed with the Medical Monitor. In the event of an urgent unrelated toxicity, study treatment should be interrupted as per [Table 5](#). Dose re-escalation is not permitted.

Table 7. Dose Modifications for Treatment-Related Toxicities (Other than Toxicities Related to Bromide)

Toxicity ^a	During Therapy	Dose Adjustment ^{b,d}
Grade 1		
All occurrences	Continue study treatment	Maintain dose level
Grade 2		
All occurrences	Continue study treatment	Maintain dose level
Grade 3^c (not including neutropenia)		
1st occurrence	Interrupt study treatment until resolved to Grade ≤1 or baseline ^b	Reduce by one dose level
2nd occurrence (same or new toxicity)		Reduce by two dose levels
3rd occurrence (same or new toxicity)	Discontinue study treatment	Not applicable
Grade 3 neutropenia (ANC: <1 – 0.5 × 10⁹/L)		
1st occurrence	Interrupt study treatment until resolved to ANC ≥1.0 × 10 ⁹ /L	Maintain dose level
2 nd occurrence		Reduce by one dose level
3rd occurrence		Reduce by two dose levels
4th occurrence	Discontinue study treatment	Not applicable
Grade 4		
All occurrences	Interrupt study treatment until resolved to Grade ≤1 or baseline and discuss with Medical Monitor	Pending discussion with Medical Monitor

Abbreviations: ANC= absolute neutrophil count, BID= twice daily

- a. Excluding alopecia and nausea, vomiting or diarrhea not receiving adequate treatment.
- b. A delay of tazemetostat for more than 14 days due to any toxicity must be discussed with the Medical Monitor before treatment can be resumed.
- c. Exclude Grades 2 and 3 anemia: Subjects are allowed to continue tazemetostat at their current dose level.
- d. If more than 2 dose modifications are required, contact Medical Monitor to discuss risk:benefit ratio of continuing on study.

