6.5.2 Dose Modification Due to Bromide Toxicity

For toxicities determined to be related to bromide, [Table 8](#) should be used for dose modifications.

Table 8. Dose Modifications for Toxicities Related to Bromide

Bromide Level	Neurologic Findings ^a	Dose Adjustment ^{b,c}
10-50 mg/dL	None	Continue
	Grade 1	Discuss with Medical Monitor possibility of dose reduction by one dose level
	Grade 2	Reduce one dose level
	Grade 3 and above	
 Interrupt dosing and discuss with Medical Monitor increased frequency of bromide monitoring and potential for restarting treatment Treatment may be restarted if approved by the Medical Monitor Reduce by at least one dose level if treatment is restarted
>50-75 mg/dL	None	Continue
	Grade 1	Discuss with Medical Monitor possibility of dose reduction
	Grade 2 and above	
 Interrupt dosing and discuss with Medical Monitor increased frequency of bromide monitoring and potential for restarting treatment Treatment may be restarted if approved by the Medical Monitor Reduce by one dose level if treatment is restarted
	Grade 3 and above	
 Interrupt dosing and discuss with Medical Monitor increased frequency of bromide monitoring and potential for restarting treatment Treatment may be restarted if approved by the Medical Monitor Reduce by at least one dose level if treatment is restarted
>75 mg/dL	None	
 Discuss with Medical Monitor increased frequency of bromide monitoring and potential need for dose reduction. Reduce by one dose level if deemed appropriate
	Grade 1	
 Discuss with Medical Monitor increased frequency of bromide monitoring and potential need for dose interruption and dose reduction by one dose level
	Grade 2	
 Interrupt dosing and discuss with Medical Monitor increased frequency of bromide monitoring and potential for restarting treatment. Treatment may be restarted if approved by the Medical Monitor Reduce by one dose level if treatment is restarted.
	Grade 3 and above	
 Interrupt dosing and discuss with Medical Monitor increased frequency of bromide monitoring and potential for restarting treatment Treatment may be restarted if approved by the Medical Monitor Reduce by at least one dose level if treatment is restarted

[figure not shown]

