6.7 Continuation of Treatment

In subjects who do not have evidence of clinical or radiographic disease progression and who do not experience unacceptable toxicity, additional cycles of tazemetostat beyond Cycle 1 may be given at the Investigator's discretion with the subject's or his/her legal representative consent.

Prior to declaring progressive disease, the Investigator should be certain that special circumstances on progression defined by RECIST 1.1 are not met. In these situations of equivocal findings of progression, subjects may continue treatment until the next scheduled disease assessment. If progression is confirmed, the date of the previous assessment will be used as the date of disease progression.

The required hematologic parameters for continuation of treatment for the second and subsequent cycles are the following:

- Platelet count must be $\geq 50 \times 10^9/L$
- ANC $\geq 1.0 \times 10^9/L$, and
- Any Grade 3 or higher toxicity must have resolved to Grade 1 or baseline

Study treatment may be interrupted for up to 14 days. Treatment interruptions longer than 14 days need Medical Monitor approval to proceed.

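### Expansion subjects starting at 520 mg/m² BID may not be dose-modified under Protocol 6.5, yet the mandatory reduction cells in Tables 7 and 8 make no exception for them and no lower expansion level is defined

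*Protocol*

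**What the plan says.** Protocol 5.3 sets the starting dose for newly enrolled subjects: "For new patients that are non-ATRT, the starting dose will be 520" mg/m² BID, while new patients with ATRT, or with an INI1-negative tumor involving the CNS, start at 1200 mg/m² BID. Cohorts 1 and 4 are closed; Cohorts 2 and 3 are open.

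The last bullet of Protocol 6.5 concerns the 520 mg/m² expansion starters. It says that "in the dose expansion portion, no dose modifications are permitted", that "dosing may be interrupted for up to 14 days to allow resolution of AEs", and that "subjects must be discontinued if the AE does not resolve with dose interruption".

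The general rules follow. For treatment-related toxicity, Table 7 (6.5.1) has cells reading "Reduce by one dose level" and others ordering a two-level reduction. For bromide-related toxicity, Table 8 (6.5.2) has "Reduce one dose level" in one cell, and a reduction on restart in others.

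On long interruptions, 6.5 says of subjects generally that they "may restart treatment with tazemetostat after consultation with the Medical Monitor". Footnote b of Table 7 requires a toxicity-related delay of more than 14 days to be discussed with the Medical Monitor before resumption. Section 6.7 says: "Treatment interruptions longer than 14 days need Medical Monitor approval to proceed".

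**The concern.** A site treating a 520 mg/m² starter with a first related Grade 3 event reads in 6.5 that the dose may not be changed, then in Table 7 that it must be lowered one level. If the site follows the table, there is no expansion level to move to. This is a safety rule for children in the two open cohorts, so an instruction that cannot be carried out as written matters in itself.

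It also matters for the data. SAP 14.1 counts subjects with dose reductions, interruptions and discontinuations due to adverse events, SAP 14.2 derives compliance, and SAP 17.1 tabulates adverse events leading to each action. If sites resolve the text differently, these outputs will partly reflect the reading chosen and not only tolerability.

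**Working it through.** No arithmetic formula applies and the plan states no figure to reproduce. The check sets the passages side by side.

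**Step 1: cells that order a reduction.**

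| Trigger | Table 7 or 8 | 520 bullet in 6.5 |
|---|---|---|
| First related Grade 3 event, not neutropenia | Interrupt to Grade ≤1 or baseline, then down one level | No modification; interrupt up to 14 days; discontinue if unresolved |
| Second such event | Down two levels | Same |
| Second Grade 3 neutropenia | Down one level | Same |
| Third Grade 3 neutropenia | Down two levels | Same |
| Bromide 10–50 mg/dL, Grade 2 neurologic finding | Down one level | Same |
| Bromide 10–50 mg/dL, Grade 3 and above; >50–75 mg/dL, Grade 2 and above and Grade 3 and above; >75 mg/dL, Grade 2 and Grade 3 and above | Interrupt; if restarted, down one or at least one level | Same |

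That is four cells in Table 7. In Table 8 it is 1 + 5 = 6 of 12 cells, five of them conditional on restart.

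**Step 2: cells and events that do not conflict on reduction.** First Grade 3 neutropenia keeps the dose. Grade 3 anemia is exempt (Table 7, footnote c). Section 6.5 exempts listed transient or quickly resolving non-hematologic events. The third non-neutropenia and fourth neutropenia occurrences lead to discontinuation. Grade 4 events await discussion. The other six Table 8 cells say continue, discuss, or reduce only if judged appropriate.

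**Step 3: is there an exception?** Neither table, its introductory text nor its footnotes restricts it to 1200 mg/m² starters or excludes 520 mg/m² starters.

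**Step 4: is there a level to reduce to?** Table 6 lists 1200, 900, 700 and 520 mg/m² BID and is assigned to 1200 mg/m² starters. Levels below 520: 0. Table 4 has four lower levels (400, 300, 240, 120), but 6.5 assigns it to escalation subjects. The tables ask for one or two levels where none is defined.

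**Step 5: interruptions beyond 14 days.** Suppose a related event resolves on day 18 of interruption. Footnote b allows resumption after discussion, the general paragraph of 6.5 after consultation, and 6.7 after approval. The bullet allows 14 days and then requires discontinuation for an event that interruption has not resolved. The three general passages also differ among themselves on what the Medical Monitor must do.

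**Step 6: the pointer.** Section 6.5.1 twice sends the reader to Table 5, which holds the Rolling 6 escalation parameters. The toxicity rules are in Table 7.

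**The case against.** The best reply is that the specific rule governs the general one. The bullet is the only text addressed to this group; it precedes the tables; and 6.5 allocates a ladder to escalation subjects and to 1200 mg/m² starters but none to 520 mg/m² starters. On that reading a reduction is simply unavailable to them. This is plausible, and it reduces the seriousness of the fault. But no passage states it, and 6.5.1 and 6.5.2 present their tables without qualification. The bullet also does not define resolution or deal with recurrence, both of which Table 7 does.

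On long interruptions, it can be said that the general sentences serve other subjects and interruptions not caused by adverse events, such as those for palliative radiotherapy (7.4), and that the bullet never mentions restart after 14 days. The latter is true, so this is a lack of fit and not two opposed statements; hence its secondary place. But footnote b covers delays caused by any toxicity, so the general passages cannot be confined to interruptions for other reasons.

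It is also fair that few subjects may be affected. Protocol 1.6.5 names platelet count decreased (3 subjects) and thrombocytopenia (2) as the most common events leading to reduction; if these are different subjects, that is 3 + 2 = 5 of 90 for those two terms. Bromide elevation was reported in 3 of 90, with no events suggestive of bromide toxicity. These figures are not split by starting dose. Section 1.6.2 also reports raised chloride, treated there as bromide interference, in 4 of 6 subjects at 520 mg/m², so bromide monitoring is relevant at this dose.

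**Conclusion.** The point holds for the ten cells in step 1: the bullet forbids what they order, no exception is written, and no expansion dose is defined for the step. The misfit over interruptions beyond 14 days is a secondary finding. How many subjects are affected cannot be derived, because the documents do not give the number starting at 520 mg/m² or their event rates.

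A reader might infer four stronger things that the documents do not support:

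- That every related Grade 3 event is affected. Step 2 shows otherwise.
- That reducing, resuming unchanged and discontinuing are three rival rules. The last two are outcomes of one rule in the bullet, according to whether the event resolves; resumption is implied there. Only reduction contradicts it.
- That 520 mg/m² is the start for everyone still enrolling. New patients with CNS involvement start at 1200 mg/m².
- That the primary analysis is undermined. Response is analysed in all treated subjects with missing or non-evaluable counted as non-response (Protocol 14.3.1, 14.4.1), and neither the 20 per cohort nor the 3-of-20 criterion depends on the modification rule.

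The conclusion rests on the text alone. It assumes that no pharmacy manual or site instruction settles the matter.

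**What to change.** The sponsor should reconcile 6.5, Table 7 (with footnote b), Table 8 and 6.7 so that one rule clearly applies to 520 mg/m² starters, including after more than 14 days of interruption, and state that rule in the tables themselves. The reference to Table 5 in 6.5.1 should become Table 7. Which rule is adopted is a clinical decision for the sponsor.

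For the analysis, report dose reductions, interruptions and discontinuations by starting dose. Cohorts 2 and 3 can mix 520 and 1200 mg/m² starters, and SAP 17.1 reports adverse events by study part and overall. SAP 14 mentions dose level and cohort for exposure, but SAP 6.1 groups expansion subjects by cohort, so a split by starting dose within expansion is not assured.

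The cost is a clarifying protocol amendment and one more breakdown of tables already planned. No new data collection or change in sample size is needed.

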6.5.1 Dose Modification due to Toxicity Not Related to Bromide

Other toxicities that, in the opinion of the Investigator are possible, probably, or definitely related to study treatment, should be managed per [Table 5](#). Toxicities that are felt by the Investigator to be unrelated to tazemetostat but clinically significant should be discussed with the Medical Monitor. In the event of an urgent unrelated toxicity, study treatment should be interrupted as per [Table 5](#). Dose re-escalation is not permitted.

Table 7. Dose Modifications for Treatment-Related Toxicities (Other than Toxicities Related to Bromide)

Toxicity ^a	During Therapy	Dose Adjustment ^{b,d}
Grade 1		
All occurrences	Continue study treatment	Maintain dose level
Grade 2		
All occurrences	Continue study treatment	Maintain dose level
Grade 3^c (not including neutropenia)		
1st occurrence	Interrupt study treatment until resolved to Grade ≤1 or baseline ^b	Reduce by one dose level
2nd occurrence (same or new toxicity)		Reduce by two dose levels
3rd occurrence (same or new toxicity)	Discontinue study treatment	Not applicable
Grade 3 neutropenia (ANC: <1 – 0.5 × 10⁹/L)		
1st occurrence	Interrupt study treatment until resolved to ANC ≥1.0 × 10 ⁹ /L	Maintain dose level
2 nd occurrence		Reduce by one dose level
3rd occurrence		Reduce by two dose levels
4th occurrence	Discontinue study treatment	Not applicable
Grade 4		
All occurrences	Interrupt study treatment until resolved to Grade ≤1 or baseline and discuss with Medical Monitor	Pending discussion with Medical Monitor

Abbreviations: ANC= absolute neutrophil count, BID= twice daily

- a. Excluding alopecia and nausea, vomiting or diarrhea not receiving adequate treatment.
- b. A delay of tazemetostat for more than 14 days due to any toxicity must be discussed with the Medical Monitor before treatment can be resumed.
- c. Exclude Grades 2 and 3 anemia: Subjects are allowed to continue tazemetostat at their current dose level.
- d. If more than 2 dose modifications are required, contact Medical Monitor to discuss risk:benefit ratio of continuing on study.

6.5.2 Dose Modification Due to Bromide Toxicity

For toxicities determined to be related to bromide, [Table 8](#) should be used for dose modifications.

Table 8. Dose Modifications for Toxicities Related to Bromide

Bromide Level	Neurologic Findings ^a	Dose Adjustment ^{b,c}
10-50 mg/dL	None	Continue
	Grade 1	Discuss with Medical Monitor possibility of dose reduction by one dose level
	Grade 2	Reduce one dose level
	Grade 3 and above	
 Interrupt dosing and discuss with Medical Monitor increased frequency of bromide monitoring and potential for restarting treatment Treatment may be restarted if approved by the Medical Monitor Reduce by at least one dose level if treatment is restarted
>50-75 mg/dL	None	Continue
	Grade 1	Discuss with Medical Monitor possibility of dose reduction
	Grade 2 and above	
 Interrupt dosing and discuss with Medical Monitor increased frequency of bromide monitoring and potential for restarting treatment Treatment may be restarted if approved by the Medical Monitor Reduce by one dose level if treatment is restarted
	Grade 3 and above	
 Interrupt dosing and discuss with Medical Monitor increased frequency of bromide monitoring and potential for restarting treatment Treatment may be restarted if approved by the Medical Monitor Reduce by at least one dose level if treatment is restarted
>75 mg/dL	None	
 Discuss with Medical Monitor increased frequency of bromide monitoring and potential need for dose reduction. Reduce by one dose level if deemed appropriate
	Grade 1	
 Discuss with Medical Monitor increased frequency of bromide monitoring and potential need for dose interruption and dose reduction by one dose level
	Grade 2	
 Interrupt dosing and discuss with Medical Monitor increased frequency of bromide monitoring and potential for restarting treatment. Treatment may be restarted if approved by the Medical Monitor Reduce by one dose level if treatment is restarted.
	Grade 3 and above	
 Interrupt dosing and discuss with Medical Monitor increased frequency of bromide monitoring and potential for restarting treatment Treatment may be restarted if approved by the Medical Monitor Reduce by at least one dose level if treatment is restarted

[figure not shown]
- Neurologic signs or symptoms not related to disease under study or concomitant medication
- If the Investigator believes a dose modification or interruption is warranted but not specified in the table above, the Medical Monitor should be contacted to discuss the appropriate treatment plan.
- If more than 2 dose modifications are required, contact Medical Monitor to discuss risk: benefit ratio of continuing on study.

6.5.3 Dose Modification due to Risk of Adverse Events of Special Interest

6.5.3.1 Dose Modification After Complete or Partial Response

For all responding patients (with CR or PR), regardless of indication, the dose will be either reduced to 520 mg/m² BID, or stopped at one year from the first observed response based on the treating Investigator’s decision. Patients will remain on study, and upon disease progression, may be rechallenged with treatment at a dose of 520 mg/m² BID for non ATRT patients, or at dose 1200 mg/m² BID for patients with ATRT or any INI1-negative tumors with CNS involvement. Overall treatment should not exceed 2 years of cumulative dosing (Figure 3).

Figure 3 Dose Modification Schematic for Patients With Complete or Partial Response

[figure not shown]

Abbreviations: ATRT= atypical teratoid tumor, CNS= central nervous system, CR= complete response, INI1= Integrase interactor 1, PD= progressive disease.

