6.5.3.2 Dose Modification for Patients with Stable Disease

For patients with SD, regardless of indication, after completion of one year of treatment from Cycle 1, Day 1, they will undergo a tumor assessment and discontinue treatment. Patients will remain on study, and upon disease progression, may be rechallenged with treatment at a dose of 520 mg/m² BID (for non-ATRT patients) or at a dose of 1200 mg/m² BID (for ATRT or any INI1-negative tumors with CNS involvement), based on the treating Investigator’s decision. Overall treatment should not exceed 2 years of cumulative dosing (Figure 4).

Figure 4 Dose Modification Schematic for Patients With Stable Disease

Abbreviations: ATRT= atypical teratoid rhabdoid tumor, BID= twice daily, C1D1= Cycle 1, Day 1, CNS= central nervous system, CR= complete response, INI1= integrase interactor 1, PD = progressive disease, PR= partial response, SD= stable disease.

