 - Epithelioid malignant peripheral nerve sheath tumor
 - Extraskelatal myxoid chondrosarcoma
 - Myoepithelial carcinoma
 - Renal medullary carcinoma
 - Chordoma (poorly differentiated or de-differentiated)
 - Other INI1-negative malignant tumors with Sponsor approval
- Cohort 4 – approximately 12 subjects with one of the tumor types defined in Cohorts 1 through 3 or synovial sarcoma with SS18-SSX rearrangement

Subjects enrolled in cohorts 1-3 will receive the RP2D of 1200 mg/m² BID of tazemetostat in oral suspension. Subjects enrolled in cohort 4 will initially receive 800 mg/m² TID (2400 mg/m²/day) of tazemetostat administered as tablets, with the possibility to switch to BID tablet dosing or suspension dosing in subsequent cycles if unable to comply with the TID schedule. Cohort 4 was added to evaluate the administration of the tazemetostat tablet formulation in pediatric subjects who can swallow tablets, which may be more palatable.

Escalation and Expansion

Subjects will discontinue study treatment at the time of disease progression, development of an unacceptable toxicity, withdrawal of consent by subject and/or parent, or after 2 years of cumulative dosing or termination of the study.

Subjects also will undergo medical history assessment, physical examinations (PEs); vital sign measurements; echocardiogram (ECHO); performance status (Lansky/Karnofsky) assessments, blood sample collection for hematology, chemistry, PK, and PD markers; electrocardiograms (ECGs); adverse event (AE) assessments; concomitant medication assessments; and pregnancy testing for females of childbearing potential.

The study duration is approximately 24 months for each subject. The duration of screening for each subject will be approximately 14 days. The subject accrual period is planned for approximately 15 months. The duration of treatment will vary for each subject. Subjects may receive tazemetostat for a cumulative maximum of 2 years. Subjects will be followed for safety for approximately 30 days after the last dose of tazemetostat. For subjects that discontinue dosing, participation will continue for survival follow-up and response for 2 years from first dose of tazemetostat.

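### Section 6.5.3 permits rechallenge of ATRT/CNS subjects at 1200 mg/m² BID without regard to an earlier toxicity reduction, while Section 6.5.1 forbids dose re-escalation; the protocol does not say which rule governs

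*Protocol*

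**What the plan says.** **Toxicity reductions.** Protocol Section 6.5 (Table 6) gives three steps below a 1200 mg/m² BID start: 900, 700 and 520. Table 7 in Section 6.5.1 handles related Grade 3 toxicity other than neutropenia with "Reduce by one dose level" at the first occurrence and "Reduce by two dose levels" at the second. The text above the table adds: "Dose re-escalation is not permitted". That section covers toxicity not related to bromide. Section 6.5.2 and Table 8 cover bromide and contain no such sentence.

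**Rechallenge.** Section 6.5.3 addresses the risk of adverse events of special interest. For responders, Section 6.5.3.1 says: "Patients will remain on study, and upon disease progression, may be rechallenged with treatment at a dose of 520 mg/m² BID for non ATRT patients". The ATRT/CNS group gets a different dose in the same sentence: "or at dose 1200 mg/m² BID for patients with ATRT or any INI1-negative tumors with CNS involvement". For stable disease, Section 6.5.3.2 sets the same two doses, and its ATRT/CNS clause reads: "or at a dose of 1200 mg/m² BID (for ATRT or any INI1-negative tumors with CNS involvement), based on the treating Investigator’s decision". Tumour class alone sets the dose. Neither section mentions a previous toxicity reduction, the dose last taken, or Section 6.5.1. Section 6.6 caps cumulative treatment at two years and does not address precedence.

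**SAP.** Section 3.1 says: "Subjects will discontinue study treatment at the time of disease progression". The SAP does not mention rechallenge. Section 14.1 measures exposure from first to last dose without removing interruptions, and Section 14.2 builds compliance on that duration.

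**The concern.** Consider a subject with CNS disease who starts at 1200 mg/m² BID, is reduced to 700 for related Grade 3 non-bromide toxicity, stops at one year with stable disease and later progresses. Section 6.5.3.2 permits rechallenge at 1200 and names no other dose for this subject. Section 6.5.1, on its plain wording, rules out going back up. An investigator cannot tell from the protocol which instruction applies.

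The first consequence concerns safety. Followed as written, Section 6.5.3 permits a child's return to the dose at which a dose-reducing toxicity occurred. The second is interpretability. Two sites could read the rules differently for the same history, and the SAP has no rechallenge period within which to separate the resulting exposure and adverse events.

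**Working it through.** The documents state no figure for this point, so the check is a comparison of text, followed by simple ratios.

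**1. Who meets both rules.** A subject needs a reduction under Section 6.5.1 and a listed rechallenge dose above the reduced dose. Expansion subjects who start at 520 mg/m² BID cannot have a dose reduction (Section 6.5), so they drop out. Subjects with ATRT or CNS disease who start at 1200 (Section 5.3) can be reduced, and the only rechallenge dose named for them is 1200. For them both rules apply.

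**2. Whether the text resolves it.**

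| Provision | What it does | Settles the rechallenge dose? |
|---|---|---|
| 6.5.1 | Bars going back up; no exception; term not defined | No |
| 6.5.3.1, 6.5.3.2 | Permit 1200 for ATRT/CNS; no condition on dose history | No |
| 6.6 | Two-year cumulative cap | No |
| 6.5, 6.7, Table 7 notes b and d | Medical Monitor involvement after interruptions over 14 days or more than two modifications | No dose named |
| 6.5.2, Table 8 | Bromide reductions; no bar on going back up | Silent |

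**3. Size of the step.** Ratio = 1200 / reduced dose. For exposure, ratio = 29,700 / Day 15 geometric mean AUC(0-24) at the reduced dose, from protocol Table 2 (ng·h/mL).

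| Reduced dose (mg/m² BID) | Dose ratio | AUC(0-24) | AUC ratio |
|---|---|---|---|
| 900 | 1200/900 = 1.33 | 21,000 | 1.41 |
| 700 | 1200/700 = 1.71 | 8,140 | 3.65 |
| 520 | 1200/520 = 2.31 | 12,500 | 2.38 |

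The AUC ratios are only indicative. Each group has 5 or 6 subjects, the values are preliminary, and the mean at 700 lies below the mean at 520. The dose ratios are the reliable measure.

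**4. Effect on SAP exposure and compliance.** SAP 14.1: duration = last dose date − first dose date + 1. Take a stable-disease subject with 52 weeks on drug, *g* weeks off and *r* weeks of rechallenge, who takes every dose at a constant assigned amount. True time on drug is 52 + *r*, SAP duration is 52 + *g* + *r*, and SAP compliance = (52 + *r*) / (52 + *g* + *r*). The documents do not give *g* or *r*. I assume *r* = 8 (one assessment interval) and vary *g*:

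| Weeks off (assumed) | On drug | SAP duration | SAP compliance |
|---|---|---|---|
| 8 | 60 | 68 | 60/68 = 88.2% |
| 24 | 60 | 84 | 60/84 = 71.4% |
| 52 | 60 | 112 | 60/112 = 53.6% |

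A fully adherent child could fall into any of the three SAP categories below 90%. SAP 17.1 also runs treatment emergence to 30 days after the end of study drug. If that end is the last rechallenge dose, the whole planned break counts as treatment-emergent time.

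**The case against.** The strongest answer is that the rules can coexist. Rechallenge is optional in both sections, and Section 6.5.3.2 leaves it to the investigator, so a permission and a prohibition can both be obeyed by not rechallenging. Restarting after a planned stop may also not be re-escalation at all. If a planned stop counts as an interruption, the Medical Monitor would be involved. These points reduce the practical risk. They do not remove the conflict, because no other dose is named for these subjects, the term is undefined, and the Medical Monitor provisions do not say which rule to apply.

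Rarity also counts. Section 1.6.5 reports that the commonest events leading to dose reduction affected 3 and 2 of 90 children. Table 1 gives 13% response and 20% stable disease among 85. A subject must be in the ATRT/CNS group, have a non-bromide reduction, keep disease control to the one-year rule, progress, and then be selected for rechallenge. Cohort 1 is closed.

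A reader might infer more than the documents support:

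- *That returning to 1200 after a bromide reduction is forbidden.* The bar appears only in the non-bromide section; Section 6.5.2 is silent.
- *That a responder reduced to 520 at one year and rechallenged at 1200 breaches the bar.* Section 6.5.3.1 sets both steps in one self-contained rule, and that reduction is not for toxicity.
- *That escalation subjects treated at 240, 300 or 400 are re-escalated by a 520 rechallenge.* If never reduced, they have nothing to re-escalate from. This is a gap in the text, not a contradiction.
- *That the SAP prohibits rechallenge.* SAP 3.1 repeats the general treat-to-progression wording of protocol Sections 3.1 and 6.8 and says nothing on rechallenge.
- *That efficacy results are compromised.* ORR counts responses only up to progression, and PFS and duration of response end there, so a response after rechallenge does not enter them.

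**Conclusion.** The conflict stands in a narrow form. For an ATRT/CNS subject reduced from 1200 mg/m² BID for toxicity not related to bromide, Section 6.5.1 bars an increase that Sections 6.5.3.1 and 6.5.3.2 permit. The increase is 1.33- to 2.31-fold in dose. After a bromide-related reduction the protocol gives no instruction either way.

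The number affected cannot be calculated from the documents and is probably small. The conclusion assumes that rechallenge at a higher dose than the one last tolerated falls under the bar; the text neither confirms nor excludes this. Figures 3 and 4 and Sections 10.4.1 and 10.4.2 were not available in the text I read, so a qualifier there cannot be ruled out.

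The SAP consequence is secondary but concrete: planned time off drug enters exposure, dose intensity and compliance, and adverse events in a rechallenge period have no rule tying them to the dose taken. The SAP does list dose interruptions and modifications, so the information is recoverable. The point should be corrected, but it does not undermine the trial's primary results.

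**What to change.** **Protocol.** Reconcile Sections 6.5.1, 6.5.3.1 and 6.5.3.2, and Figures 3 and 4 if needed. State which rule governs rechallenge for a subject with an earlier toxicity reduction, and separately for one with a bromide-related reduction. Say whether restarting after a planned stop counts as re-escalation. The choice of rule belongs to the sponsor's clinicians.

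**SAP.** Add a sentence to Section 3.1 recognising that treatment may resume after progression under protocol Section 6.5.3. Add a rechallenge-period flag to the exposure and adverse event datasets. Use it to leave the planned off-treatment interval out of duration, dose intensity and compliance (Sections 14.1 and 14.2), and to attribute adverse events to the dose taken.

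**Cost.** A short protocol clarification or amendment text, one SAP sentence and one derived flag. No new data and no additional subjects.
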